Contact lens wearers often report dry eye symptoms and show signs of MGD including gland atrophy, thinned lipid layer, and increased tear film instability.⁶⁻⁸ It has been shown that in many patients with intolerance to contact lenses, MGD has been observed. Therefore, treatment of MGD may support functioning of the meibomian glands and lead to improvement in patient contact lens comfort. Warm compresses are a commonly prescribed treatment method for applying localized heat to the meibomian glands to improve secretion.⁹⁻¹¹ With good patient compliance, warm compresses have been shown to be an adequate supplemental therapy for MGD as the heat softens meibum in glands that are obstructed allowing for secretion into the tear film. Many methods of applying heat to the eyelids for treatment of MGD exist; however, the results of the different methods can vary based on the heating method, how long the compress is applied, and whether the compress remains hot for the duration of application. Because of the sometimes seemingly ineffectiveness of the therapy due to variation in methods and no accepted standard, patient compliance for home therapy often wanes and further reduces the likelihood of successful treatment. Therefore, the purpose of this study is to assess the potential benefits of using the Bruder Moist Heat Compress, a warm compress capable of maintain heat effectively, in contact lens wearers with MGD.

Study Design & Endpoints

This will be a prospective, three-arm, randomized controlled study to evaluate the benefits of using the Bruder Moist Heat Compress in contact lens wearers who report reduced comfortable wearing time by assessing improvement in MG function and comfortable contact lens wearing time after one month of daily warm compress application. All subjects will undergo examination to determine eligibility and capture baseline status. Study endpoints will be evaluated after one month.

Thirty adults who currently wear contact lenses, who report reduced contact lens wear time will be enrolled in the study. Subjects will be randomized to either one of two treatment arms or a control arm with approximately ten subjects per group; that is, subjects will be randomized to one of the following study arms:

- 1) Application of Bruder Moist Heat Compress twice daily for one month (ten minute application in the morning prior to contact lens insertion and ten minute application in the evening after lens removal)

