- 2) Application of Bruder Moist Heat Compress once daily for one month (ten minute application in the evening after lens removal)
- 3) Application of warm wash cloth twice daily (ten minute application each time) for one month (control group)

Subjects will be seen for three study visits over a period of four weeks according to the following visit schedule:

- Visit 1 (Screening & Randomization, Day 1)
- Visit 2 (Day 15 \pm 2 days)
- Visit 3 (Final Visit, Day 29 \pm 1 day)

The procedures to be performed during the visits include:

1. Questionnaires: CLDEQ long form, SPEED, OSDI
2. Medical and Ophthalmic History
3. Habitual visual acuity with contact lenses
4. Contact Lens fit assessment
5. LipiView to measure tear film thickness
6. Slit lamp examination
7. Tear film break up time
8. Corneal Staining
9. MG assessment
10. Meibography
11. Corneal Topography

Each visit will take approximately 45 minutes. Subjects will be instructed to apply the Bruder Moist Heat Compress after removal or prior to insertion of contact lenses. Subjects will heat the compress according to the instructions on the package, namely: heat for twenty-five seconds in the microwave, and depending on the microwave wattage increase by increments of five seconds to not exceed a total of thirty-five seconds. Once heated, subjects will apply the compress to closed eyelids for ten minutes. During the treatment period, subjects will complete a daily diary that captures insertion and removal time of contact lenses, as well as the time comfortable contact lens wear ends. Diaries will also be used to ensure subject compliance of application of the Bruder compress.

Study Objectives

Primary Objective: To show that daily application of the Bruder Moist Heat Compress in subjects with MGD who experience CL discomfort can result in an increase in comfortable contact lens wear time

Secondary Objective: To compare the efficacy of once daily application of the Bruder Moist Heat Compress versus twice daily application

Tertiary Objective: To show that the Bruder Moist Heat Compress is an effective treatment for improving meibomian gland function in symptomatic contact lens wearers

Study Endpoints

Primary: Mean change from baseline in the duration of subject-reported comfortable contact lens daily wear time (hours per day) at the week four visit

Secondary: Mean change in comfortable contact lens wear time (hours per day) in twice daily application group compared to once daily application group

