Tertiary: Mean change in total meibomian gland score in treatment groups using the Bruder Moist Heat Compress compared to controls from baseline to four weeks

Inclusion Criteria:

1. 18 years or older
2. Provide informed consent and authorization to disclose protected health information
3. Have habitual contact lens corrected visual acuity in each eye of at least 20/30
4. Willing to comply with protocol
5. Wear soft daily contact lenses for total wear time of at least 4 hours a day and at least 4 days a week on average over at least a 30 day period before enrollment
6. Have a diagnosis of Contact Lens Dry Eye based on the CLDEQ results
7. Have at least a 2 hour difference between overall wear time and comfortable wear time of contact lenses
8. Assess that the contact lens fit/material/disinfection solution are acceptable and not reasons for CL discomfort

Exclusion Criteria:

1. Have any uncontrolled systemic disease that in the investigator's opinion could be expected to interfere with the study, for example, conditions associated with dry eye disease
2. Pregnant by self-report
3. Active ocular conditions: infection, allergic conjunctivitis, severe eyelid inflammation including anterior blepharitis
4. Have a clinically significant ophthalmic abnormality noted during examination or per subject history
5. Have changed the brand of contact lenses or care solutions within 30 days prior to screening or anticipates the need to change current type or brand of contact lenses or care solutions
6. Any overnight wear of contact lenses or daily disposable contact lenses
7. Require use of prescribed topical ophthalmic medications
8. Participation in a clinical trial in the past 30 days
9. Any previous refractive or corneal surgery (e.g., PRK, LASIK, radial keratotomy, etc.)
10. In the opinion of the investigator, be unwilling or unable to comply with the study protocol
11. Have temporary and/or permanent punctal plugs in either or both eyes
12. Have initiated or altered the dosage of omega-3 dietary supplements in the past 30 days

References

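### Does the tertiary endpoint go wrong by comparing both Bruder groups with a twice-daily wash cloth without singling out the frequency-matched pair?

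*Protocol*

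**What the plan says.** Study Design & Endpoints defines three arms of about ten subjects each, 30 in all:

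- Arm 1: "Application of Bruder Moist Heat Compress twice daily for one month", ten minutes each time.
- Arm 2: "Application of Bruder Moist Heat Compress once daily for one month (ten minute application in the evening after lens removal".
- Arm 3: "Application of warm wash cloth twice daily (ten minute application each time) for one month (control group".

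The same section describes arms 1 and 2 as treatment arms and arm 3 as the control arm. Under Study Objectives, the secondary objective is "To compare the efficacy of once daily application of the Bruder Moist Heat Compress versus twice daily application" and the tertiary objective is "To show that the Bruder Moist Heat Compress is an effective treatment for improving meibomian gland function in symptomatic contact lens wearers". Under Study Endpoints, the tertiary endpoint is "Mean change in total meibomian gland score in treatment groups using the Bruder Moist Heat Compress compared to controls from baseline to four weeks". The secondary endpoint, on comfortable wear time, sets the twice-daily Bruder group against the once-daily one. The protocol gives no alpha, power, effect size or standard deviation for any endpoint.

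**The concern.** The tertiary endpoint is the only one that names controls, so the comparison of the compress with the wash cloth rests on its wording. That wording does not say whether the two Bruder arms are taken separately or together. Arms 1 and 3 differ only in device. Arms 2 and 3 differ in device and also in daily heating time.

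The protocol itself gives reason to think frequency could matter. The secondary objective treats it as an open question, and the background says "the results of the different methods can vary based on the heating method, how long the compress is applied". If once-daily use is less effective, a pooled Bruder group would understate the device effect at equal frequency. A null pooled result could not, on its own, tell an ineffective device from too few applications. Leaving the contrast open could also allow a choice after the results are known.

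**Working it through.** **The plan's own figure.** 3 arms × 10 = 30, which agrees with the stated total. There is no power figure to reproduce.

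**Daily heating time, from the arm definitions.** Arm 1: 2 × 10 = 20 minutes. Arm 2: 1 × 10 = 10 minutes. Arm 3: 2 × 10 = 20 minutes. Arms 1 and 3 are matched, so the design is not confounded.

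**What each contrast estimates.** Let D be the device effect at equal frequency and F the loss from using the compress once a day instead of twice. Both are assumed, in SD units of the change score.

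- Arm 1 v arm 3: D
- Arm 2 v arm 3: D − F
- Pooled Bruder v arm 3, equal arm sizes: [D + (D − F)]/2 = D − F/2

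The pooled contrast is the average of the two separate ones. All three come from the same gland scores, so the endpoint wording loses no data.

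**Precision.** The standard error factor is √(1/10 + 1/10) = 0.447 for 10 v 10 and √(1/20 + 1/10) = 0.387 for 20 v 10. The ratio is 0.447/0.387 = 1.155, so the matched pair carries a standard error about 15% larger.

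**Power.** Two-sample t-test, noncentral t, two-sided alpha 0.05 (assumed), no baseline adjustment, noncentrality = effect / standard error factor.

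| D (SD) | F (SD) | Arm 1 v arm 3 | Pooled v arm 3 | Arm 2 v arm 3 |
|---|---|---|---|---|
| 1.0 | 0 | 0.562 | 0.703 | 0.562 |
| 1.0 | 0.2 | 0.562 | 0.612 | 0.395 |
| 1.0 | 0.3 | 0.562 | 0.563 | 0.317 |
| 1.0 | 0.5 | 0.562 | 0.464 | 0.185 |
| 1.0 | 1.0 | 0.562 | 0.239 | 0.050 |

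At D = 0.5 the matched pair has power 0.185. Pooling has 0.239, 0.169 and 0.096 at F = 0, 0.2 and 0.5.

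**Break-even.** By normal approximation, (D − F/2)/0.387 = D/0.447 gives F/D = 2 × (1 − 0.866) = 0.27. With the t distribution and 28 v 18 degrees of freedom, F = 0.302 at D = 1.0 and 0.151 at D = 0.5, so about 0.30 D. Below that point pooling has more power; above it the matched pair does.

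**Reading the text against this.** The design names two treatment arms and a control, and the endpoint then speaks of Bruder treatment groups in the plural. The natural reading is two comparisons, each Bruder group with control. The first is the matched pair. The second differs in frequency, as the arm labels show openly. No sentence calls for pooling.

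**The case for a change.** The strongest case for the concern is that the protocol does fix comparisons at endpoint level: the secondary endpoint names its pair. The tertiary objective is a claim about the device, and only arm 1 v arm 3 holds frequency constant. On this view the fault lies in what is written, and one sentence would remove a choice that is otherwise open after the data are seen.

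Part of this stands. The wording does permit more than one reading, and the readings estimate different quantities if F is not zero. It would be reasonable to ask that the analysis plan say whether the Bruder groups are compared separately or pooled.

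The rest does not carry. The secondary endpoint has only one possible pair, so naming it settles nothing about pooling. The tertiary endpoint gives variable, time point, active groups and comparator, which is comparable detail. The tertiary objective asks whether the compress is effective and sets no condition of equal frequency. Whether either Bruder regimen does better than the twice-daily wash cloth is a legitimate question. The difficulty of interpreting a null pooled result arises only if the pooled result is reported alone, which the protocol does not prescribe.

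**Conclusion.** The concern does not hold. The endpoint states nothing false and contradicts no other part of the protocol. The matched contrast exists in the design, falls within the natural reading of the endpoint and can be estimated from the planned data. What is open is its rank beside the once-daily and pooled contrasts, and that commonly belongs in a statistical analysis plan.

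Making the matched pair the lead contrast would be a trade-off and not a correction. At D = 1 SD it lowers power from 70% to 56% if F = 0, and raises it from 46% to 56% if F = 0.5 SD. Nothing in the protocol shows which side of the break-even, about 0.3 D, applies.

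These figures rest on ten evaluable subjects per arm, two-sided alpha 0.05, unadjusted t-tests and assumed D and F. That the once-daily and pooled contrasts err against the device also assumes F is not negative. The matter touches a tertiary endpoint only; the primary and secondary endpoints are unaffected.

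### Do Inclusion 5 and Exclusion 6 leave it undecided whether daily-disposable lens wearers may enter the trial?

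*Protocol*

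**What the plan says.** Four eligibility criteria in the protocol bear on lens type.

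- Inclusion 5 requires that subjects "Wear soft daily contact lenses for total wear time of at least 4 hours a day", on at least 4 days a week over at least 30 days before enrolment.
- Inclusion 8 reads "Assess that the contact lens fit/material/disinfection solution are acceptable and not reasons for CL discomfort".
- Exclusion 5 removes subjects who "Have changed the brand of contact lenses or care solutions within 30 days prior to screening", or who expect to need such a change.
- Exclusion 6 reads, in full, "Any overnight wear of contact lenses or daily disposable contact lenses".

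The Study Design & Endpoints section names no lens type: "Thirty adults who currently wear contact lenses, who report reduced contact lens wear time will be enrolled in the study", with "approximately ten subjects per group". No section defines *daily* as applied to lenses.

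**The concern.** In Inclusion 5, *daily* could describe how the lens is worn (in by day, out at night) or what it is (used once and discarded). In Exclusion 6, a wearing habit and a lens type are joined by *or* without a second verb. The phrase about overnight wear could therefore govern only the first noun or both. One pair of readings has the inclusion list asking for the lens that the exclusion list forbids. Another pair lets the same subject in.

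The primary endpoint is change in comfortable lens wear time in hours per day, and the protocol itself takes care to hold lens factors steady through Inclusion 8 and Exclusion 5. An unclear rule on lens type seems to undercut that care. In a trial of thirty, a few subjects admitted under a different reading would be a visible share of an arm and would blur the population to which the result applies.

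**Working it through.** The protocol gives no figure to reproduce on this point. The check is to cross the possible readings and see which of them the rest of the text supports.

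**Crossing the readings for a wearer of single-use lenses**

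| Inclusion 5: meaning of *daily* | Exclusion 6: scope | Outcome |
|---|---|---|
| Worn by day, removed at night | Overnight wear, and separately all disposables | Excluded |
| Worn by day, removed at night | Overnight wear only, of either lens | Allowed |
| Single-use | Overnight wear only, of either lens | Required |
| Single-use | Overnight wear, and separately all disposables | Nobody eligible |

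All four are grammatically possible. They are not equally supported.

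**Testing each against the text**

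1. *Nobody eligible.* No reader would adopt a reading under which the trial cannot enrol.
2. *Required.* When the protocol means single-use lenses, it says daily disposable (Exclusion 6). Inclusion 5 uses a different term, which suggests a different meaning. The primary endpoint also applies *daily* to wear time. A rule requiring single-use lenses would fit badly with Inclusion 8, which has the disinfection solution assessed, and with Exclusion 5, which concerns care solutions.
3. *Allowed.* This needs Exclusion 6 to forbid overnight wear of contact lenses or overnight wear of daily disposables. Disposables are contact lenses, so the first part already covers the second, and the last words of the criterion would do nothing.
4. *Excluded.* Every word of Exclusion 6 has a function, the terms in Inclusion 5 and Exclusion 6 are consistent with each other, and the references to solutions in Inclusion 8 and Exclusion 5 make sense.

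Only the fourth of these passes every test.

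**Size if the line were misread**

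With about ten subjects per arm and thirty in all, one subject admitted on another reading is 1/10 = 10% of an arm and 1/30 = 3.3% of the trial. The document gives neither the lens mix at the clinic nor an effect of lens type on wear time. The number affected and any shift in the endpoint therefore cannot be calculated. The 10% figure would apply equally to any single eligibility slip.

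**Direction of any error**

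The protocol has subjects examined for eligibility and then randomized, and the primary endpoint is a change from baseline. A misread criterion acts before assignment and on all arms alike. It can add variability, chance imbalance or a small shift in the population, but it does not favour one arm systematically.

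**The case for a change.** The best argument for acting is that eligibility rules should not need inference. A screener has to work out the meaning from references to solutions in other criteria, and neither of those criteria says that reusable lenses are required. A single-use wearer who uses no solution could pass both. Eligibility is also protocol content, which cannot be left to a statistical analysis plan. No stratification by lens type is mentioned, so a chance imbalance in so small a trial would not be restrained by design. Clearer wording would cost two lines.

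Much of this stands. *Daily* is undefined, Exclusion 6 is badly built, and the protocol does treat lens fit, material, brand and solution as able to affect comfort.

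What does not stand is the step from loose wording to a flaw in the trial. The reading that excludes disposables does not depend on the solution criteria alone; it follows from Exclusion 6 itself, since any other reading leaves half the sentence empty. That lens type, single-use against reusable, would alter the change in comfortable wear time is plausible, but the protocol gives no evidence or figure for it. Any count of affected subjects is likewise an assumption. Rewording the criteria to exclude disposables would restate the rule that the text already yields. Rewording them to admit disposables would be a different trial population, and nothing in the document shows that it would be a better one.

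**Conclusion.** The concern does not call for a change. It describes a real looseness of wording, but the evident rule is reusable soft lenses worn by day, with overnight wear and daily disposables each excluded. Followed on that reading, the protocol gives a coherent population and leaves the primary comparison intact. Matching the terms in the two criteria and listing the two exclusions separately would be a courtesy to the screener. It would not alter the endpoint, the sample size or any comparison.

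The size is at most 10% of an arm per subject misadmitted, with an unknown count and no systematic direction. This rests on two assumptions: that staff read Exclusion 6 so that all its words have a function, and that eligibility is decided before, and without knowledge of, the arm a subject will receive.
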